8.3.2 Analysis of the Secondary Endpoints

This study will report feasibility metrics associated with the implementation of CALM remotely in a primary central nervous system tumor population, including compliance, eligibility, accrual, adverse effects, study completion, and participant satisfaction with the intervention. If attrition is less than 20% of enrolled participants, this study is considered feasible. If 50% of participants report satisfaction with the intervention on the WIWI it will be considered feasible.

To describe the effects of the CALM intervention on death anxiety we will calculate total scores, subscale scores, and/or t-scores (if applicable) for the Death and Dying Distress completed at varying time points (baseline, month 3, and month 6). This data will be summarized by time point quantitatively and graphically. To quantify the immediate CALM effect, we will calculate the effect size difference between baseline scores and month 3. To quantify the long-term CALM effect, we will calculate the effect size differences between baseline and month 6.

Previous data on death anxiety reported by advanced cancer participants who underwent CALM showed a reduction of 8 (SD of the difference=15.7). With 80 participants, we have 99% power to detect this difference using a two-tailed test at a 5% significance level. To determine whether there is sufficient power to demonstrate reductions in psychological distress and psychological well-being, we need preliminary data on these variables that is due to the CALM treatment. In the absence of preliminary data, we cannot provide statements about the statistical power of these secondary endpoints. However, this study will generate preliminary data that will inform future studies.

To evaluate the feasibility of implementing CALM remotely, we will use descriptive statistics to summarize information, including rates of compliance and attrition, and participant satisfaction. This will be evaluated at the interim analysis using the same percentages outlined for the final analysis. The quantity of missing data, the variability of the data over time, and trends over time will be especially important to report to assess the feasibility of CALM. We will report participant satisfaction with the CALM experience using the responses from the WIWI instrument and thematic analysis of participant responses from the interviews. Participant's responses will go through a multi-stage process of categorizing and coding to identify themes associated with the participants experience with the CALM intervention. Results of the analysis will be reported out separately.

We will consider the study to be feasible if the following criteria are met:

- Accrual: Recruitment of 100 participants to have 80 evaluable participants in two years and less than 20% of eligible participants unable to participate due to lack of electronic devices (computer, smartphone, or iPad).
- Compliance: at least 80% of participants completing the outcome measures at all time points

Tolerability and acceptability will be assessed through the WIWI.

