3.6 OFF-STUDY CRITERIA

- Completion of treatment and follow up
- Participant noncompliance
- Participant requests to be withdrawn from the study
- Lost to follow-up
- Death
- PI decision to close the study
- Permanent loss of ability to consent

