8.2 SAMPLE SIZE DETERMINATION

The primary objective of this study is to demonstrate the reduction of depressive symptoms from baseline to 6 months using CALM in PCNST participants. Based on the previous study, we expect a mean difference reduction in depressive symptoms of 1.8 with a standard deviation of the difference of 5.7. To detect this difference, we need 80 participants using a 2-tailed test at 5 significance level and 80% power. To account for estimated attrition of 20%, recruitment of 100 participants to have 80 evaluable participants.

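### The planned loss of 20 in 100 meets the plan's 80-evaluable target but misses its attrition cut-off, and neither the attrition nor the compliance rule says how deaths and loss of capacity count.

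*Combined protocol and SAP*

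**What the plan says.** Section 8.2 sets the numbers: "To account for estimated attrition of 20%, recruitment of 100 participants to have 80 evaluable participants".

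Section 8.3.2 then gives several feasibility rules:

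- **Attrition**, in its own sentence: "If attrition is less than 20% of enrolled participants, this study is considered feasible". The denominator is everyone enrolled, and attrition is not defined.
- **Accrual**, in a list of criteria further down: the same 100 recruited and 80 evaluable, within two years, plus a limit on exclusions for lack of a device.
- **Compliance**, in the same list: "at least 80% of participants completing the outcome measures at all time points". Whether the denominator is all enrolled or those still on study is not stated.
- **Satisfaction**, in its own sentence: a 50% threshold on the WIWI.

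The same percentages apply at the interim analysis. The list containing accrual and compliance does not mention attrition, and nothing says whether all the rules must be met together.

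Section 3.6 lists death and "Permanent loss of ability to consent" among the off-study reasons, alongside withdrawal, noncompliance and loss to follow-up. Section 2.1.1 admits participants with a life expectancy of at least 3 months, while the primary outcome is at 6 months.

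**The concern.** The attrition cut-off sits at the loss the plan expects, and it is a strict inequality. The result for which the trial was sized does not satisfy it, although the same result satisfies the evaluable-number target. The compliance cut-off is the mirror image. If it is taken over all enrolled and 20% have left with their forms incomplete, every remaining participant must complete every time point. The plan foresees missed material: section 3.2 provides reminders for unreturned assessments, and section 6.1 lets a participant stop questionnaires while continuing therapy.

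The second difficulty is what the rules measure. With no exemption for death or permanent loss of capacity, disease progression is scored together with failure to deliver the therapy remotely. Section 3.1 says the team will try to recruit an adequate share of participants with recurrence, so the result would also move with case mix.

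Feasibility is a secondary objective, and section 1.2.2 says the study is to inform a multicenter randomized trial. A rule that is close to even odds when everything goes to plan tells the designers of that trial little.

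**Working it through.** **Inputs from the plan.** Enrolled 100, evaluable 80, attrition 20%, mean change 1.8, SD of the difference 5.7, two-sided 5%, power 80% (all section 8.2). Attrition below 20% of enrolled and compliance of at least 80% (section 8.3.2).

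**Inputs assumed.** Losses are independent between participants. The return rate r per form and the split between dropout and disease-related loss are not in the documents, so ranges are shown.

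**1. The plan's own figures.** n = ((1.960 + 0.842) × 5.7/1.8)² = 78.7, so 79. The noncentral t gives 81, with 79.7% power at 80. Then 80/(1 − 0.20) = 100. The sample size reproduces.

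**2. The planned result against the rules.** With 20 of 100 lost, 80 are evaluable, so the target is met. Attrition is 20/100 = 20%, which is not below 20%, so the attrition rule is missed. No probability model is needed for this.

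**3. Attrition rule when true loss is 20%.** Passing means at most 19 lost.

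- Final analysis: P(X ≤ 19 | 100, 0.20) = 0.460, so it is missed with probability 0.540.
- Interim: P(X ≤ 9 | 50, 0.20) = 0.444, or P(X ≤ 7 | 40, 0.20) = 0.437, depending on whether half means 50 enrolled or 40 evaluable.
- For an 80% chance of passing at the final analysis, true loss would have to be about 16.4%.

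**4. Compliance rule over all enrolled.** Passing means at least 80 of 100 complete. Let q be the probability that an enrolled participant completes all time points.

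| Assumption | q | P(at least 80 of 100) |
|---|---|---|
| All retained participants return everything | 0.80 | 0.56 |
| One further form at risk, r = 97% | 0.80 × 0.97 = 0.776 | 0.33 |
| One further form at risk, r = 95% | 0.80 × 0.95 = 0.760 | 0.21 |
| Two forms at risk, r = 97% | 0.80 × 0.97² = 0.753 | 0.16 |
| Two forms at risk, r = 95% | 0.80 × 0.95² = 0.722 | 0.05 |

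The one-form rows apply if a missing month-6 form is already inside the planned 20%, leaving only month 3 at risk. The two-form rows apply if the 20% covers only participants who leave the study.

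**5. Compliance over those on study.** With 80 on study and two forms at risk, P(X ≥ 64 | 80, 0.95² = 0.9025) = 0.998, and P(X ≥ 64 | 80, 0.85² = 0.7225) = 0.07. This denominator still separates good from poor completion.

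**6. Attrition rule on dropout only.** Suppose part of the planned 20 points is death or loss of capacity.

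| True dropout | P(at most 19) | P(at most 20) |
|---|---|---|
| 20% | 0.46 | 0.56 |
| 18% | 0.66 | 0.75 |
| 16% | 0.83 | 0.89 |
| 14% | 0.94 | 0.96 |
| 12% | 0.985 | 0.993 |
| 30% | 0.009 | 0.017 |

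**7. Precision.** The exact 95% interval for 20/100 is 12.7% to 29.2%.

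**The case against.** The strongest objection is that the figures do not add up to a verdict on the study. A reader might infer that a trial running exactly to plan is more likely than not to be called infeasible. That requires attrition to be a necessary criterion. The attrition sentence is worded as a condition that is enough for feasibility, and the later list omits it. On that list alone, 80 completers of 100 meets both the evaluable target and the compliance rule, and compliance passes with probability 0.56 when returns are complete. This objection stands.

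A reader might also infer that compliance is nearly certain to fail on the plan's own assumptions. The plan assumes no return rate; the low probabilities rest on assumed rates, and the lowest may charge month 6 twice. Nor is it certain that 20% attrition caps completion at 80%, because section 6.1 lets participants stop therapy but continue questionnaires. Section 9.4.1.1 lets participants skip questions, but nothing says a skipped item makes a measure incomplete. These limits also stand.

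A third tempting reading is that the plan counts deaths as failures. No sentence says so. It follows only from an undefined term, a denominator of all enrolled and the absence of an exemption. Three months is a minimum life expectancy, participants on surveillance are eligible, and no mortality figure is given. The planned 20% may already include deaths, so the 0.46 does not depend on this point.

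Finally, asking for performance better than planned can be a deliberate choice. That would be defensible if stated, but here the same section also counts the planned yield as success.

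**Conclusion.** The concern holds in a limited form. The clash between the attrition cut-off and the 80-of-100 target is plain from the text. At a true 20% loss the attrition rule passes with probability 0.46, assuming independent losses and 100 enrolled. Compliance over all enrolled has no slack at that loss: 0.56 with complete returns, 0.21 to 0.33 with one further form at risk, and 0.05 to 0.16 with two, at assumed return rates of 95% to 97%. Whether missing the attrition rule makes the study infeasible cannot be determined from the documents. That deaths and loss of capacity count against remote delivery is a literal reading, not a stated rule. The sample-size arithmetic is sound. The plan should be changed, but the primary analysis is unaffected.

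**What to change.** Amend section 8.3.2 as follows.

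1. Reconcile the attrition cut-off with the 80-of-100 target, for example by wording it as no more than 20%, and state whether it is a required criterion.
2. Apply it to withdrawal, noncompliance and loss to follow-up. Report death and permanent loss of capacity separately, with all-cause attrition beside them.
3. Compute compliance over participants alive and on study at each time point, and report completion over all enrolled beside it.
4. Give each rate an exact 95% confidence interval.

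The cost is wording and a few more table rows, since section 3.6 already distinguishes the off-study reasons. Two attrition and two completion figures must be reported. All-cause attrition and completion over all enrolled need to stay visible, because the on-study denominator removes people who withdrew, including any who withdrew through dissatisfaction.

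Step 1 removes the contradiction but raises the pass probability only to 0.56 if the planned 20% is all dropout. Step 2 makes the rule more lenient by an amount that depends on the unknown split: under the present cut-off of at most 19, it passes with probability 0.66, 0.83, 0.94 or 0.985 at 18%, 16%, 14% or 12% dropout. It still passes with probability of only 0.009 at 30% dropout (0.017 if 20 losses are allowed).

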1.1.2 Secondary Objectives

- To demonstrate the short-term effects of the CALM intervention in the reduction of depressive symptoms using the PROMIS-Depression scale in PCNST participants from baseline to 3 months.
- To determine the effects of the CALM intervention on death anxiety using the Death and Dying Distress Scale at both 3 and 6 months, compared to baseline.
- To describe the feasibility of implementing CALM remotely in a PCNST population, including eligibility, accrual, compliance, adverse effects, study completion, and participant satisfaction with the intervention.

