2.1.2 Exclusion Criteria

- Participants without access to a smartphone, computer, or tablet to complete remote sessions.

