2.1.3 Recruitment Strategies

Participants will be recruited from the Natural History Study (NHS) # 16C0151 by invitation. This protocol may be abstracted into a plain language announcement that will be posted on NIH websites and on NIH social media platforms. Any recruitment materials will be submitted to the IRB for review prior to implementation.

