2.2.2 Screening activities performed after consent for screening has been signed

No additional screening activities are required.

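### As worded, the device-access half of the Accrual feasibility criterion (section 8.3.2) is met automatically, because section 2.1.2 makes anyone without a device ineligible

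*Combined protocol and SAP*

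**What the plan says.** Section 1.1.2 sets a secondary objective: "To describe the feasibility of implementing CALM remotely in a PCNST population, including eligibility, accrual, compliance", among other items. Section 8.3.2 repeats the list of metrics to be reported, "including compliance, eligibility, accrual, adverse effects, study completion, and participant satisfaction with the intervention", and then gives pass/fail criteria. The Accrual criterion has two halves. The first is "Recruitment of 100 participants to have 80 evaluable participants in two years". The second is "less than 20% of eligible participants unable to participate due to lack of electronic devices", with the devices listed as computer, smartphone or iPad.

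Section 2.1.2 contains a single exclusion: "Participants without access to a smartphone, computer, or tablet to complete remote sessions".

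On recruitment and screening, section 2.1.3 says "Participants will be recruited from the Natural History Study (NHS) # 16C0151 by invitation". Section 2.2.1 allows contact with prospective subjects and record review before consent. Section 2.2.2 says of the period after consent: "No additional screening activities are required". None of these sections mentions a log of people turned away or of the reasons.

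**The concern.** The criterion is a share of *eligible* people, but eligibility in this protocol already requires a device. A team applying sections 2.1.2 and 8.3.2 as they stand removes every person without a device before the share is taken. The criterion then reports the effect of the exclusion rule and carries no information about access in the patient population.

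This is the only pass/fail item that addresses whether patients can reach remote delivery at all. Compliance, attrition and satisfaction are measured in people who already have a device. Section 3.1 makes every study procedure remote, and section 1.2.2 says the results will feed the planning of a multicenter randomized study. A figure of 0% by construction could be carried into that planning as if it had been observed.

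**Working it through.** **Figures in the plan.** The 20% device cut-off is a chosen threshold with no derivation to reproduce. The other half of the Accrual criterion does reproduce. From section 8.2 (difference 1.8, SD of the difference 5.7, two-sided 5%, 80% power), the normal approximation gives n = (5.7 × (1.960 + 0.842) / 1.8)² = 78.7, so 79. The t-based calculation gives 81, and power at 80 is 79.7%. Allowing for 20% attrition, 80 / (1 − 0.20) = 100. Those targets stand.

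**The device criterion under two denominators.** Let E be the number who meet every criterion, including having a device, and D the number who meet every criterion except having a device. The documents give neither; the values below are assumed.

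- As worded: (eligible and without a device) / eligible = 0 / E = 0% for any D.
- Among the otherwise eligible: D / (E + D).

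| D (assumed), with E = 100 | As worded | D / (E + D) | Result on the second basis |
|---|---|---|---|
| 0 | 0/100 = 0% | 0/100 = 0% | pass |
| 10 | 0/100 = 0% | 10/110 = 9.1% | pass |
| 24 | 0/100 = 0% | 24/124 = 19.4% | pass |
| 25 | 0/100 = 0% | 25/125 = 20.0% | fail (not below 20%) |
| 50 | 0/100 = 0% | 50/150 = 33.3% | fail |
| 100 | 0/100 = 0% | 100/200 = 50.0% | fail |

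**How the trigger depends on E.** D / (E + D) reaches 20% when D = E / 4. The plan's 100 is a recruitment target, and the number of eligible device-holders may be larger. If 100 are enrolled and a fraction u of eligible device-holders take part, E = 100 / u:

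- u = 100% (assumed): E = 100, failure from D = 25
- u = 75%: E = 133.3, failure from D = 34
- u = 50%: E = 200, failure from D = 50
- u = 25%: E = 400, failure from D = 100

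**Would a reworded criterion discriminate?** Take 125 otherwise-eligible people and a binomial count with true no-device rate p (assumed). Failure means 25 or more without a device. The probability of failing is 0.1% at p = 10%, 7.9% at 15%, 53.6% at 20%, 92.1% at 25% and 99.6% at 30%. On the otherwise-eligible basis the item becomes a real test.

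**The case against.** The strongest reply is that the sentence makes sense only if *eligible* means otherwise eligible. The layout supports this: the clinical and consent criteria are in section 2.1.1, device access stands alone in 2.1.2, and the item sits under Accrual, which concerns people before enrolment. Eligibility is also a metric to be reported, so a report with reasons would be expected to show device exclusions. I accept that this was probably the intention. But no section defines the term that way, gives a denominator for the eligibility metric, or plans the count. A count not kept during recruitment may not be recoverable later.

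A reader might infer that the trial can declare remote CALM feasible whatever the state of device access. The documents do not support that. Feasibility also requires the recruitment and evaluability targets within two years, at least 80% completing the outcome measures at all time points, attrition below 20%, and 50% reporting satisfaction on the WIWI. Each of these can fail, and poor access would itself shrink the pool available for recruitment.

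A reader might also infer that the item could never fail in any circumstances. A participant who lost a device after enrolment could conceivably be counted, though that is marginal for an accrual item. The *tablet* and *iPad* mismatch does not rescue the wording: someone with another make of tablet is eligible and able to take part.

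Nor is the exclusion itself a fault. With all procedures remote, a device is necessary.

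**Conclusion.** The point holds for one item. Followed as written, the device-access half of the Accrual criterion is 0% at accrual and therefore passes, because the protocol's own eligibility rule empties the numerator. This rests on the text alone and needs no assumption about access rates.

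How far the true share might lie from 0% is unknown. The documents give no device-access rate, and nothing in them suggests that it is near 20%. The switch from pass to fail between 24 and 25 exclusions assumes 100 otherwise-eligible device-holders; the trigger rises as that number rises.

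The other feasibility criteria, the sample size and the primary analysis are unaffected. The wording should be corrected, since a pre-specified threshold ought to be able to give either answer.

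**What to change.** Replace the device half of the Accrual criterion in section 8.3.2 with wording to this effect: *fewer than 20% of contacted 16C0151 participants who are otherwise eligible at pre-consent screening (meeting the section 2.1.1 criteria that can be assessed before consent) are excluded solely under section 2.1.2 for lack of a device*.

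The limit to criteria assessable before consent matters. Section 2.1.1 includes willingness to sign consent, which cannot be judged in someone screened out beforehand. For the same reason, device-holders should enter the denominator at the same pre-consent stage, whether or not they go on to enrol.

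Record lack of a device as a reason in a pre-screening log kept during the contacts that section 2.2.1 already allows. Use one device list in sections 2.1.2 and 8.3.2. Leave the exclusion criterion as it is.

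The cost is one reworded sentence and a small logging task, with no added procedures for participants. The reported figure may be less favourable than an automatic 0%. Invitees who never reply because they have no device will still be missed, so the result should be reported as a share of those contacted and screened.

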8.3.3 Exploratory Analyses

To determine the effect of the CALM intervention on well-being, we will calculate effect size differences in well-being using between baseline and months 3 and 6.

To explore the effects of the CALM intervention on symptom burden and interference, we will report subscale scores for the MDASI-BT and MDASI-SP and the proportion of participants with 5 or greater (moderate to severe) and 7 or greater (severe) ratings on the 0-10 numeric rating scale of each symptom items for each time point. To quantify the immediate CALM effect, we will calculate the effect size difference between baseline scores and month 3. To quantify the long term CALM effect, we will calculate the effect size differences between baseline and month 6. We will fit a linear mixed model with participants as a random effect and time as a fixed effect using MDASI-BT and MDASI-SP subscale scores as a dependent variable.

To explore the effects of the CALM intervention on health status, we will perform linear mixed models and effect size calculations on health status using raw and subscale scores from the EQ-5D. To quantify the immediate CALM effect, we will calculate the effect size difference between baseline scores and month 3. To quantify the long-term CALM effect, we will calculate the effect size differences between baseline and month 6. We will fit a linear mixed model with participants as a random effect and time as a fixed effect using EQ-5D as a dependent variable.

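### For death distress, well-being and MDASI item proportions, the plan specifies neither a within-participant comparison nor a missing-data method, so selective loss can appear as a CALM effect

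*Combined protocol and SAP*

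**What the plan says.** For DADDS, a secondary outcome, section 8.3.2 states: "This data will be summarized by time point quantitatively and graphically". It then adds that "we will calculate the effect size difference between baseline scores and month 3", and does the same for month 6. It names no test, model, analysis set or missing-data method for this outcome. Its power statement rests on earlier data that "showed a reduction of 8 (SD of the difference=15.7"), and continues: "With 80 participants, we have 99% power to detect this difference using a two-tailed test at a 5% significance level".

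For well-being (QUAL-EC, ECR-M-16), section 8.3.3 gives only effect sizes from baseline to months 3 and 6.

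For MDASI, section 8.3.3 reports subscale scores, effect sizes, and the proportions at 5 or more and at 7 or more for "ratings on the 0-10 numeric rating scale of each symptom items for each time point". It also commits to a model: "We will fit a linear mixed model with participants as a random effect and time as a fixed effect using MDASI-BT and MDASI-SP subscale scores". A similar model is planned for EQ-5D. No other outcome in 8.3.2 or 8.3.3 has one.

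Section 8.2 expects 20% attrition, from 100 recruited to 80 evaluable. Section 3.6 lists death and "Permanent loss of ability to consent" among the reasons for leaving the study. Section 2.1.1 asks for a life expectancy of at least 3 months, while the last assessment is at 6 months. Section 3.1 describes a single arm and says that depression, distress and quality of life are affected by recurrence.

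**The concern.** Where a plan gives summaries by time point and names no common analysis set, the usual default is to use whoever answered at each assessment. Baseline and follow-up then describe different groups. If those who leave were worse off than those who stay, the follow-up figure can fall although nobody has changed.

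There is no control arm in which the same loss would show up, and sections 8.3.2 and 8.3.3 label the baseline-to-follow-up differences as the CALM effect. Section 1.2.2 says the results will be used to calculate the sample size and effect for a multicenter randomized study, so a distorted change would carry forward into that design.

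**Working it through.** **1. The plan's own DADDS figure.** Inputs from 8.3.2: reduction 8, SD of the difference 15.7, n = 80, two-sided 5%. Standard error = 15.7/√80 = 1.755. Power = Φ(8/1.755 − 1.960) = Φ(2.598) = 99.5%; the noncentral t gives 99.4%. The stated 99% reproduces. This is a paired calculation, since it uses the SD of within-participant differences. The attrition figure also reproduces: 80/(1 − 0.20) = 100. The arithmetic is sound; the question is which estimator will be used.

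**2. Shift in a mean when nobody changes.** Mean of all enrolled minus mean of stayers = attrition × (leaver mean − stayer mean). With 20% attrition and leavers assumed 5, 10 or 15 points higher on DADDS:
- 0.20 × 5 = 1 point, or 1/8 = 12.5% of the cited reduction
- 0.20 × 10 = 2 points, or 25%
- 0.20 × 15 = 3 points, or 37.5%

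**3. Shift in a proportion when nobody changes.** Assume 30 of 100 are severe on an item at baseline (the documents give no such figure) and 20 leave. Proportion among stayers = (30 − severe leavers)/80:
- 6 severe leavers: 24/80 = 30.0%, no shift
- 10: 20/80 = 25.0%
- 12: 18/80 = 22.5%
- 15: 15/80 = 18.8%
- 3: 27/80 = 33.8%, an apparent worsening

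**4. Comparison of estimators for DADDS.** I simulated 400,000 participants with no true change, 20% attrition and the SD of the difference fixed at 15.7. Assumptions: normal scores (the 0–75 limits are ignored); a baseline-to-follow-up correlation ρ of 0.3, 0.5 or 0.7, so that the score SD = 15.7/√(2(1 − ρ)) = 13.3, 15.7 or 20.3; and more distressed participants more likely to leave. In each cell the first figure is for odds of leaving that double per SD of severity, and the second for loss of exactly the worst 20%. Negative values are false improvement, in points.

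| Loss depends on | ρ | Follow-up responders minus all at baseline | Paired, completers only | Mixed-model type |
|---|---|---|---|---|
| Baseline score | 0.3 | −0.47, −1.34 | +1.21, +3.29 | +0.03, +0.06 |
| Baseline score | 0.5 | −1.00, −2.73 | +1.04, +2.77 | +0.02, +0.01 |
| Baseline score | 0.7 | −1.84, −4.96 | +0.77, +2.12 | −0.01, −0.01 |
| Unseen follow-up score | 0.3 | −1.66, −4.60 | −1.15, −3.21 | −1.51, −4.35 |
| Unseen follow-up score | 0.5 | −1.99, −5.47 | −0.99, −2.72 | −1.51, −4.58 |
| Unseen follow-up score | 0.7 | −2.61, −7.09 | −0.78, −2.14 | −1.38, −4.55 |

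The mixed-model column is the likelihood estimate for two time points that uses every baseline. With 10% attrition, which may be nearer the position at month 3, the time-point comparison ranges from −0.23 to −3.95.

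**5. Reading the table.** The unpaired comparison shows false improvement under both mechanisms. Pairing alone does not remove the problem: when loss depends on baseline severity it reverses the sign. The mixed model is close to zero in that case. No estimator is unbiased when loss depends on scores that were never observed.

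**The case against.** A reader might infer that the plan sets everyone enrolled at baseline against only those remaining later, and that loss of sicker participants will therefore look like improvement. The documents do not support that. No denominator is stated, so differing sets are an inference from silence. The effect sizes may well be meant as paired: the DADDS power statement uses an SD of the difference with 80 participants, the evaluable number in 8.2. Nor is it true of symptom results generally, because the MDASI subscale scores have a mixed model with a participant effect. All of this stands. It narrows the point to an unstated analysis set and unstated pairing for DADDS, the two well-being scores and the item proportions.

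The protocol also limits and monitors loss. Section 6.1 lets a participant stop therapy but continue questionnaires, section 3.2 provides reminders, and 8.3.2 will report the quantity of missing data. These measures help, but none says how missing scores enter the estimates of change.

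The outcomes affected are secondary or exploratory, and 8.3.2 frames the DADDS analysis as descriptive; the primary paired test is not part of this point. Finally, 20% attrition may be too high for MDASI. The calendar in 3.4 marks it at baseline and 3 months only, whereas 3.2 and the month-6 effect size in 8.3.3 call for a 6-month assessment. Those sections need reconciling.

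**Conclusion.** The point holds in a limited form. For DADDS, QUAL-EC, ECR-M-16 and the MDASI item proportions, the plan offers time-point summaries, effect sizes not stated to be within-participant, or both. The only longitudinal models are for other scores. Selective loss can then appear as a CALM effect; it need not.

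If the unpaired comparison is the one made and the more distressed leave, the false DADDS fall at 20% attrition is 0.5 to 7.1 points, about 6% to 89% of the cited 8 (0.47/8 and 7.09/8). The documents supply the 20%, the 8 and the 15.7. The correlations, the strength of selection, the leaver differences and the 30% severe baseline are assumptions. If leavers are healthier than stayers the shift goes the other way, and if the comparison is paired but limited to completers it can show false worsening of about 0.8 to 3.3 points. The plan should be amended, because these results are meant to inform a randomized trial and the change needs no new data.

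**What to change.** In 8.3.2 and 8.3.3:

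- Extend the mixed model already planned (participant as random effect, time as fixed effect, all available data) to DADDS, QUAL-EC and ECR-M-16, and make it the main estimate of change.
- Define the baseline-to-month-3 and baseline-to-month-6 effect sizes as within-participant.
- For the MDASI item proportions at 5 or more and at 7 or more, report the paired change among participants with both assessments.
- Beside each follow-up summary, print three baseline values: that of the same participants, that of all enrolled, and that of those who left.
- State that none of these steps removes bias if loss depends on unobserved follow-up scores.

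The cost is analysis-plan wording, a little more analysis and extra table columns.
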